10.3.8 Event-free Survival

Event-free Survival (EFS) will be defined as the number of days from randomization to the date of progressive disease, confirmed morphologic relapse from CR or CRi, treatment failure defined as failure to achieve CR, CRi or MLFS after at least 6 cycles of study treatment collected on study drug completion eCRF or death from any cause. The confirmation is required for morphologic relapse (MR). Based on the IWG criteria implemented in the protocol, if the bone marrow blasts are between 5 - 10%, a repeated bone marrow assessment should be conducted to distinguish between bone marrow regeneration and relapse. For MR with bone marrow blast $\leq 10\%$ and followed by a non-PD/non-MR response prior to start of post-treatment therapy, this MR is considered an unconfirmed MR and therefore, the subject is still considered to be a responder.

If the specified event does not occur, subjects will be censored. The detailed censoring rule is described in [Table 4](#). Data for subjects without any disease assessments performed after randomization will be censored at the time of randomization.

Table 4. Event/Censor and Corresponding Event/Censor Time for EFS

Situation	Event/Censor	Event Time/Censor Time
PD, confirmed morphologic relapse (MR),* and treatment failure events on or prior to any post-treatment therapy and data cutoff date, whichever is earliest	Event	Earliest PD, MR or treatment failure event date
Death event on or prior to data cutoff date regardless whether it occurred after any post-treatment therapy initiated	Event	Death date
No PD, confirmed MR,* treatment failure, or death events, and without post-treatment therapy initiated on or prior to the data cutoff date	Censor	Last disease assessment date (bone marrow or hematology lab collection date) on or prior to the data cutoff date
No confirmed MR,* PD, or treatment failure on or prior to post-treatment therapy initiated on or prior to the data cutoff date, and no death on or prior to data cutoff	Censor	Start date of post-treatment therapy

* An un-confirmed MR is defined as a MR with bone marrow blast $\leq 10\%$ and followed by non-PD/Non-MR prior to the post-treatment therapy. Otherwise, MR is considered to be a confirmed MR.

The distribution of EFS will be estimated for each treatment arm using Kaplan-Meier methodology and compared between treatment arms using the log-rank test stratified by AML status (de novo, secondary) and age ($18 < 75, \geq 75$). Median EFS will be calculated and 95% confidence interval for median EFS will be presented by treatment arm. The hazard ratio between treatment arms will be estimated using the Cox proportional hazards model stratified by age ($18 < 75, \geq 75$) and AML status (de novo, secondary).

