5.3.3 Efficacy Variables

Efficacy Assessments

Responses will be evaluated based on the revised guidelines by the modified International Working Group (IWG) for AML. Progressive disease is defined per European LeukemiaNet (ELN) recommendations. Subject's response is based on most recent physical examination, bone marrow results and recent hematology values. For subjects who require a delay in the next cycle of study treatment for blood count recovery after a bone marrow evaluation, hematology values up to pre-dose labs from Day 1 of the next cycle or 2 weeks from the bone marrow if there is no additional dosing can be used to determine the modified IWG response. As a significant number of the subjects in this study might have antecedent hematologic illnesses, hematologic response including transfusion independence will also be evaluated.

Criteria for evaluation are as follows:

- CR: No morphologic evidence of AML and absolute neutrophil count $\geq 10^3/\mu\text{L}$, platelets $\geq 10^5/\mu\text{L}$, red cell transfusion independence, and bone marrow with $< 5\%$ blasts, absence of circulating blasts and blasts with Auer rods; absence of extramedullary disease.
- CRi: All criteria as CR except for residual neutropenia $< 10^3/\mu\text{L}$ (1,000/ μL) or thrombocytopenia $< 10^5/\mu\text{L}$ (100,000/ μL). If all criteria for CR are met except for RBC transfusion independence, this also fulfills CRi criteria.
- PR: All of the hematologic values for a CR but with a decrease of at least 50% in the percentage of blasts to 5% to 25% in the bone marrow aspirate.

- MLFS: Less than 5% blasts in an aspirate sample with marrow spicules and with a count of at least 200 nucleated cells, absence of circulating leukemia cells, absence of extramedullary disease, and absolute neutrophils $< 10^3/\mu\text{L}$ (1,000/ μL) and thrombocytopenia $< 10^5/\mu\text{L}$ (100,000/ μL).
- RD: Failure to achieve CR, CRi, PR; in subjects surviving at least 7 days following completion of Cycle 1 treatment, with evidence of persistent leukemia by blood and/or bone marrow examination.
- MR: reappearance* of $\geq 5\%$ blasts post CR/CRi in peripheral blood or bone marrow or development of extramedullary disease.
 - * In cases with bone marrow blast percentages of 5% – 10%, a repeat marrow should be performed one week later to distinguish relapse from bone marrow regeneration.
- PD:

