 - $> 50\%$ increase in marrow blasts over baseline (a minimum 15% point increase is required in cases with $< 30\%$ blasts at baseline; or persistent marrow blast percentage of $> 70\%$ over at least 3 months; without at least a 100% improvement in ANC to an absolute level ($> 0.5 \times 10^9/\text{L}$ [500/ μL], and/or platelet count to $> 50 \times 10^9/\text{L}$ [50000/ μL] non-transfused); or
 - 50% increase in peripheral blasts ($\text{WBC} \times \% \text{ blasts}$) to $> 25 \times 10^9/\text{L}$ ($> 25000/\mu\text{L}$); or
 - New extramedullary disease

Reporting of Results

All dosed subjects will be assessed for response to treatment based on the published guidelines. Assessments will be performed at the end of Cycle 1 and every 3 cycles thereafter for response assessment. For subjects who are unblinded following the final analysis results, assessments every 3 cycles thereafter are not required. Bone marrow collection can be completed as per institutional standard of care. Subject will be assigned to one or more of the following categories by investigators:

1. complete remission;

2. complete remission with incomplete blood count recovery;
3. partial remission;
4. morphologic leukemia free state;
5. resistant disease;
6. progressive disease;
7. indeterminate (not assessable, insufficient data);
8. morphologic relapse;

MRD status if performed at investigator sites for subjects who achieve CR or CRi:

1. minimal residual disease negative;
2. minimal residual disease positive.

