10.4.2 Duration of CR + CRi

Duration of CR + CRi will be defined as the number of days from the date of first response (CR or CRi) per the modified IWG criteria for AML to the earliest evidence of confirmed morphologic relapse, progressive disease or death due to disease progression. If a subject is still responding at the data cutoff date, then the subject will be censored. The disease assessment data after the onset of any post-treatment therapy will not be included in the duration of CR + CRi analysis. The detailed censoring rule is described in Table 5. Duration of CR + CRi will be analyzed for all randomized subjects who achieve the best response of CR or CRi.

Table 5. Event/Censor and Corresponding Event/Censor Time for Duration of CR + CRi

Situation	Event/Censor	Event Time/Censor Time
Confirmed morphologic relapse (MR)* or progressive disease (PD) on or prior to any post-treatment therapy and data cutoff date, whichever is earliest	Event	Earliest MR or PD event date
Death due to disease progression on or prior to data cutoff date regardless whether it occurred after any post-treatment therapy initiated	Event	Death date
No confirmed MR, * PD, or death due to disease progression events and without post-treatment therapy initiated on or prior to the data cutoff date	Censor	Last disease assessment date (bone marrow or hematology lab collection date) on or prior to the data cutoff date
No confirmed MR, * or PD on or prior to post-treatment therapy initiated on or prior to the data cutoff date, no death due to disease progression on or prior to data cutoff date	Censor	Start date of post-treatment therapy

* An un-confirmed MR is defined as a MR with bone marrow blast $\leq 10\%$ and followed by non-PD/Non-MR prior to the post-treatment therapy. Otherwise, MR is considered to be a confirmed MR.

The distribution of duration of CR + CRi will be estimated for each treatment arm using Kaplan-Meier methodology. Median duration of CR + CRi will be calculated and 95% confidence interval for median duration of CR + CRi will be presented by treatment arm.

Analysis of modified duration of CR + CRi that includes death from all causes by the cutoff date will be performed as a sensitivity analysis.

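### The EFS and response-duration rule lets an assessment that does not show blasts below 5% cancel a low-blast morphologic relapse

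*SAP*

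**What the plan says.** SAP 10.3.8 counts a morphologic relapse (MR) as an EFS event only if it is confirmed, and gives the reason. When marrow blasts are 5–10%, "a repeated bone marrow assessment should be conducted to distinguish between bone marrow regeneration and relapse". The operative rule follows. For an MR with marrow blasts of at most 10%, if it is "followed by a non-PD/non-MR response prior to start of post-treatment therapy, this MR is considered an unconfirmed MR". The stated consequence for the analysis: "therefore, the subject is still considered to be a responder". The Table 4 footnote restates the condition as "followed by non-PD/Non-MR prior to the post-treatment therapy. Otherwise, MR is considered to be a confirmed MR", without the word *response*.

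Table 5 (SAP 10.4.2, duration of CR + CRi) carries the same footnote, opening "An un-confirmed MR is defined as a MR with bone marrow blast" and setting the same 10% limit. SAP 10.4.3 and 10.4.4 apply Table 5 to the durations of CR and of CR + CRh.

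The confirmation step comes from Protocol 5.3.3, which says of marrow blasts of 5–10% that "a repeat marrow should be performed one week later to distinguish relapse from bone marrow regeneration". That section defines MR as blasts of 5% or more after CR or CRi, in blood or in marrow, or extramedullary disease. It lists eight response categories (among them "indeterminate (not assessable, insufficient data"). It describes resistant disease as failure to reach CR, CRi or PR, assigned "in subjects surviving at least 7 days following completion of Cycle 1 treatment, with evidence of persistent leukemia by blood and/or bone marrow examination".

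**The concern.** The rule is keyed to what the later assessment is not, rather than to what it shows. Regeneration is supported when a repeat marrow is back below 5% blasts. The SAP asks only that the later entry be neither PD nor MR. It does not require a marrow, a remission category or a blast count. An entry that shows persistent blasts, or shows nothing, can then restore a relapsed subject to responder status.

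The entry test is also wider than the case the protocol addresses. It applies to any MR with marrow blasts of at most 10%, with no lower bound and no reference to other sites. An MR called on circulating blasts or extramedullary disease, with few marrow blasts, meets it as well.

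At stake is the event date, or whether there is an event at all, in EFS and in three response-duration analyses. Two programmers could also code the rule differently, because the body text and the footnotes are worded differently.

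**Working it through.** The plan gives no figure to reproduce, so the check compares the rule with the category definitions and then applies it to constructed subjects.

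**1. Which categories cancel an MR.** Categories and definitions are from Protocol 5.3.3; the cancelling test is the Table 4 and 5 footnote read literally.

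| Later category | What it implies about marrow blasts | Neither PD nor MR | Shows < 5% |
|---|---|---|---|
| CR, CRi, MLFS | below 5% | yes | yes |
| PR | 5–25% | yes | no |
| Resistant disease | persistent leukemia | yes | no |
| Indeterminate | not assessable | yes | no |
| PD, MR | – | no | – |

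Eight categories less PD and MR leaves 8 − 2 = 6 that cancel. Of these, 6 − 3 = 3 do not show clearance.

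**2. Overlap of PR and MR.** Assume 60% blasts at baseline, CR, an MR at 8%, then 9% on repeat with counts at CR level. The fall from baseline is (60 − 9)/60 = 85%, which is at least 50%, and 9% lies within 5–25%, so PR fits. But 9% after CR is also at least 5%, so MR fits too. The protocol allows a subject one or more categories, and neither document states which takes precedence.

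**3. Constructed timelines.** The days and blast counts are assumptions: CR on day 28, MR with 8% marrow blasts on day 112, and one later assessment before any post-treatment therapy. Day 196 is three 28-day cycles after day 112 (3 × 28 = 84). The comparison rule cancels only on CR, CRi or MLFS with marrow blasts below 5%.

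| Later assessment | SAP, literal | Clearance required |
|---|---|---|
| Indeterminate, day 196 | censored day 196 | event day 112 |
| Resistant disease, day 196 | censored day 196 | event day 112 |
| PR, day 196 | censored day 196 | event day 112 |
| Indeterminate day 196, death day 300 | event day 300 | event day 112 |
| MR, day 196 | event day 112 | event day 112 |
| None | event day 112 | event day 112 |
| CR on repeat marrow, day 119 | no event | no event |

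The two rules differ only where clearance was not shown. The genuine regeneration case (last row) is kept by both.

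**4. Assessments without a marrow.** Protocol 5.1.3 says that after two successive CR or CRi results, assessments are laboratory and physical examination, with a marrow on concern for relapse. The SAP does not require the cancelling assessment to be one with a marrow.

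**5. Site and lower bound.** Take an MR called on at least 5% circulating blasts with 3% in the marrow. Since 3% is at most 10%, the SAP test is met and the MR can be cancelled, yet it lies outside the 5–10% marrow case for which the protocol asks for a repeat.

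**6. What else would catch a cancelled MR.** Death still counts in EFS, as do a later PD and a later confirmed MR. Treatment failure is failure to reach CR, CRi or MLFS, which a subject already in CR or CRi has not met. The marrow criterion for PD needs more than a 50% rise over baseline: for a 60% baseline, above 60 × 1.5 = 90%. The other PD criteria remain.

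**7. Who is exposed.** An MR requires a prior CR or CRi. As an illustration only, assume the response rates in the protocol's background: 78% with the combination (Section 3.0, 18 subjects) and about 11% with LDAC (Section 3.2). The subjects to whom the rule could apply would be 0.78 × 140 ≈ 109 and 0.11 × 70 ≈ 8. These are subjects exposed, not subjects affected.

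**The case against.** Much can be said for the rule as its authors probably meant it. A repeat marrow with 5% or more blasts after CR or CRi meets the MR definition again and would normally confirm the first MR. Resistant disease is worded as failure to reach a remission, so it fits poorly after one. The body text says *response*, and an indeterminate entry is not naturally a response. *Followed by* may mean the next assessment rather than any later one. With the one-week repeat done as the protocol asks, most cases would resolve correctly. An MR with no later assessment stays confirmed, and EFS is also analysed per IRC.

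These points narrow the problem without removing it. The footnotes, which define confirmed and unconfirmed MR for the event tables, omit *response*. Nothing stops PR being recorded alone where PR and MR overlap, and no text excludes indeterminate or resistant disease.

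Some stronger inferences are not supported:

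- A reader might infer that relapses are routinely erased by any later visit. The text permits that reading but does not compel it.
- The 84-day gap in the timelines arises only if the one-week repeat is missed.
- A reader might argue that regeneration cannot explain circulating blasts. The documents do not say so. The supported point is only that the protocol ties its repeat to marrow blasts of 5–10%.
- A reader might want a fixed window such as 28 days. No such limit has a source in the documents, and it could count a subject with a later documented CR as relapsed.

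**Conclusion.** The concern holds as a defect in a stated rule. On its literal text, SAP 10.3.8 with the Table 4 and 5 footnotes lets PR, resistant disease, an indeterminate entry or an assessment without a marrow cancel a low-blast MR. It also lets MRs called on blood or extramedullary disease be cancelled. Both go beyond the purpose the SAP itself states.

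The reach is limited. The effect is a delayed or censored event in EFS, which is last in the standard ranking (14th in Table 7, 16th in Table 8), and in response durations that are exploratory and have no between-arm test specified. OS is unaffected. So are the any-time response rates, because a later MR does not change them.

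A reader might infer that EFS is biased towards venetoclax by a material amount. The documents do not support that. They support only that responders alone are exposed, and that any such cancellation lengthens EFS or response duration. They give no frequency of MR with marrow blasts of at most 10%, nor of the entries that could follow it, so the number of subjects and the size of any bias cannot be derived.

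**What to change.** In SAP 10.3.8 and in the footnotes of Tables 4 and 5, use one definition:

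- An unconfirmed MR is one based only on marrow blasts of 5–10%, where the next evaluable marrow before post-treatment therapy shows less than 5% blasts (CR, CRi or MLFS).
- PR, resistant disease and indeterminate do not cancel an MR.
- Every other MR is an event at its first date.

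No fixed window is needed. A sensitivity analysis counting every MR at its first date would show how much the confirmation rule matters.

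The cost is wording and programming. Marrow blasts are already used by the rule, and blood blast counts, where detected, are among the laboratory tests. The documents do not show whether the basis of each MR (marrow, blood or extramedullary) is a separate field, so that should be checked. A few more relapse events may count, and EFS and response durations may become slightly less favourable. Protocol 1.1 records that the final efficacy analysis has been performed, so any re-analysis with the revised rule would have to be labelled post hoc.

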EFS will be defined as the number of days from randomization to the date of progressive disease, relapse from CR to CRi, treatment failure defined as failure to achieve CR, CRi, PR, or MFLS, or death from any cause. If a specified event does not occur, subjects will be censored at the date of last disease assessment. Data for subjects without any disease assessments performed after randomization will be censored at the date of randomization. The distribution of EFS will be estimated for each treatment arm using Kaplan-Meier methodology and compared between treatment arms using the log-rank test stratified by AML status (secondary, de novo) and age ($18 - < 75, \geq 75$).

Post baseline transfusion independence rate will be calculated as the portion of subjects who achieved transfusion independence post baseline. Transfusion independence is defined as a period of at least 56 days with no transfusion between the first dose of study drug and the last dose of study drug plus 30 days. In addition, the rate of conversion will be calculated as proportion of subjects being post-baseline transfusion independent from baseline transfusion dependence. The transfusion independence rate will be evaluated for 1) RBC and 2) platelets. All randomized subjects will be included to estimate the post-baseline transfusion independence rate.

Post baseline transfusion independence rate will be estimated as the proportion of subjects known to achieve transfusion independence during the evaluation period. Transfusion independence rate will be compared between treatment arms using CMH test stratified by AML status (secondary, de novo) and age ($18 - < 75, \geq 75$). In addition, 95% confidence interval will be constructed for transfusion independence rate.

The rates of conversion from baseline transfusion dependence to post-baseline transfusion independence will be estimated. The conversion rate will be evaluated for 1) RBC and 2) platelets.

The proportion of subjects with complete remission or complete remission with partial hematologic recovery (CR + CRh) by the initiation of Cycle 2 will be calculated. CR + CRh rate by the initiation of Cycle 2 will be compared between treatment arms using CMH test stratified by AML status (secondary, de novo) and age ($18 < 75, \geq 75$). In addition, 95% confidence interval will be constructed for CR + CRh rate by the initiation of Cycle 2.

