10.0 Efficacy Analysis

10.1 General Considerations

Unless otherwise noted, for all statistical analysis, statistical significance will be determined by a two-sided P value ≤ 0.05 (when rounded to three decimal places).

When the 133st death in the full analysis set occurs, there will be a final review of the eCRF data. After the data collection is completed and reviewed for completeness and all data management quality assurance (QA) and quality control (QC) procedures are performed, the study blind will be broken and clinical database data will be extracted for documentation and statistical analyses of the efficacy and safety data. Efficacy analyses will be performed on the full analysis set.

Unless otherwise specified, the primary analysis of all response/progression related endpoints (e.g., CR/CRi) will be based on the investigator assessment. Sensitivity analyses will be performed based on Independent Review Committee's assessment.

For the analysis of all response/progression related endpoints, MRD response rate, and transfusion independence rate, the data collected after the data cutoff date or initiation of post treatment therapy, whichever comes earlier, will be excluded.

Censoring Dates for Prematurely Blind Broken Subjects

For all efficacy endpoints except OS, if the subject's blind has prematurely broken by sites before "Cutoff" date, the date of premature blind break will be set as "Cutoff" date for the subject.

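### SAP Table 4 handles event-free patients who start new therapy according to their later outcome, so EFS censoring depends on the future

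*SAP*

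**What the plan says.** SAP 10.3.8 says of EFS "The detailed censoring rule is described in" Table 4. Two of its four rows concern patients who start post-treatment therapy before any progression (PD), confirmed relapse or treatment failure.

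- Row 2, "Death event on or prior to data cutoff date regardless whether it occurred after any post-treatment therapy initiated": an event at the date of death.
- Row 4, "No confirmed MR,* PD, or treatment failure on or prior to post-treatment therapy initiated on or prior to the data cutoff date", with the further condition that the patient has not died by cutoff: censored on the day the new therapy started.

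The EFS distribution is then "estimated for each treatment arm using Kaplan-Meier methodology and compared between treatment arms using the log-rank test", stratified, with a stratified Cox hazard ratio.

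Two other texts bear on this. Protocol 8.1.4.2 includes "or death from any cause" in the EFS definition and states "If a specified event does not occur, subjects will be censored at the date of last disease assessment"; it has no censoring at new therapy. SAP 10.1 says that for response and progression endpoints "the data collected after the data cutoff date or initiation of post treatment therapy, whichever comes earlier, will be excluded". Row 2 agrees with the first text and row 4 with the second.

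The only other planned EFS analysis is the independent-review version in SAP 10.5, for which no different censoring rule is stated. The additional analyses in SAP 10.6 do not include EFS.

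**The concern.** Counting deaths after new therapy is a recognised rule, and so is censoring at new therapy. Table 4 chooses between them for each patient by looking at survival to cutoff. Once patients have switched, the risk set contains only those who will die by cutoff. Membership of the risk set then depends on the future, and the censoring is informative by construction.

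At stake are the reported EFS medians, the EFS hazard ratio and the EFS test. EFS is listed last in both hierarchies in SAP 10.7 (14th for the EU, 16th for the US). Footnote b, however, moves subgroup endpoints below EFS when the subgroup has fewer than 30 patients or an allocation above 3:1, so EFS can gate those endpoints.

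**Working it through.** **The plan's own figure.** The documents give no power or event figure for EFS. The OS figure reproduces: with 133 deaths, 2:1 allocation and HR 0.545, Schoenfeld power is Φ(√(133 × 2/9) × |ln 0.545| − 1.96) = Φ(3.30 − 1.96) = 0.91. With one Lan-DeMets O'Brien-Fleming look at 100 of 133 deaths it is 0.904, and the one-sided boundaries are 0.0097 and 0.0221 (SAP Table 1: 0.010 and 0.022). Nothing below changes this.

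**Two patients.** A and B both switch event-free at month 3; cutoff is month 12. A dies at month 8: at risk to month 8, event (row 2). B is alive at month 12: removed at month 3 (row 4).

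**Kaplan-Meier, exact.** Compare Table 4 with the same events at the same times and survivors kept at risk to cutoff. Each risk set under Table 4 is a subset, so every factor 1 − d/n is smaller or equal and the curve can never be higher. Illustration: ten patients switch at month 3; five die one by one and five are alive at cutoff. Table 4 gives (4/5)(3/4)(2/3)(1/2)(0) = 0. Keeping survivors at risk gives (9/10)(8/9)(7/8)(6/7)(5/6) = 0.5.

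**Post-switch death rate.** For exponential survival with rate λ and T months from switch to cutoff, Table 4 estimates λ(1 − e^(−λT)) / (1 − e^(−λT)(1 + λT)). With T = 12 (assumed):
- median 6 months: 0.215 per month against a true 0.116 (1.9-fold);
- median 11 months: 0.190 against 0.063 (3.0-fold).

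**Simulation under no effect.** 140 v 70 patients, uniform accrual over 15 months (assumed), cutoff at the 133rd death, unstratified log-rank, 20,000 trials per scenario, switching does not alter hazards. All PD and switching hazards (per month) are assumptions. Death median is 9 months in both arms. The last two columns give the one-sided error in favour of venetoclax under Table 4, ungated, nominal 0.025.

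| Switching, control / venetoclax | Event-free switchers (PD 0.05) | PD 0.05 | No PD |
|---|---|---|---|
| 0.045 / 0.03 | 23% v 16% | 0.036 | 0.049 |
| 0.06 / 0.03 | 29% v 16% | 0.044 | 0.077 |
| 0.06 / 0.02 | 29% v 11% | 0.050 | 0.102 |
| 0.09 / 0.03 | 38% v 16% | 0.061 | 0.157 |
| 0.10 / 0.02 | 41% v 11% | 0.074 | 0.239 |

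- Equal switching: 0.028 to 0.029.
- Venetoclax switching more: 0.001 to 0.022 in favour, 0.032 to 0.258 against.
- PD 0.12, control switching more: 0.024 to 0.036, depending on the death rate after PD.
- Either consistent rule (count everything, or censor every switcher) in all these runs: 0.026 to 0.031.
- Half of each arm resistant, and mainly those patients switching: Table 4 0.024 to 0.031; count everything 0.027 to 0.028; censor every switcher 0.008 to 0.080.

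A repeat gave 0.049 and 0.064 (PD 0.05) and 0.108 and 0.155 (no PD) for the two 3-fold rows. A separate model with more frequent PD (median 9 months each for death and for PD, relapse or failure, switching 0.06 / 0.02) gave a smaller shift: error 3.6% against 2.9%, HR 0.977 against 0.997.

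**Medians (months).** No PD, true 9.0: Table 4 gives 7.5 to 8.2 on control and 8.4 to 8.6 on venetoclax when control switches more, and 8.0 in both arms at equal switching of 0.06. PD 0.05, true 5.46: 5.31 to 5.43. PD 0.12, true 4.08: control 4.15 to 4.30, too high, because row 2 moves a PD after the switch to the later death date.

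**Design effect** (death medians 6 v 11, true EFS HR 0.545). Table 4 HR: 0.537 to 0.545 when control switches more, 0.555 to 0.571 at equal hazard, 0.579 to 0.605 when venetoclax switches more. In the last case power is 0.91 to 0.85, against 0.97 when all events count.

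**The case against.** - *Table 4 applies both texts: drop disease assessments after new therapy, keep deaths.* This explains where the rows come from. But if later deaths count, the survivors must stay at risk of death, and row 4 removes them. Counting only deaths after the switch with survivors kept to cutoff would be uniform, yet not neutral: in the separate model it moved the null HR to 1.093 or 0.913 under unequal switching.
- *The large error rates need no PD and 3- to 5-fold switching differences.* This stands. EFS includes PD, relapse and treatment failure, and at PD 0.12 the error is near nominal.
- *Censoring every switcher is no better.* This stands in part. It drops deaths that both documents define as events, and when mainly resistant patients switch it does worse than Table 4 (0.008 to 0.080 against 0.024 to 0.031). It should not be the default primary rule.
- *The final analysis is done.* Protocol 1.1 says so. That limits the remedy to supplementary analyses; it does not remove the defect.

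A reader might infer that Table 4 always makes medians too low, or always favours venetoclax. Neither is supported: the first holds only against the comparator that keeps survivors at risk without PD after the switch, and the second depends on which arm switches more.

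**Conclusion.** The defect is structural and certain from the text: censoring of event-free switchers depends on whether they later die. Its size is uncertain. Under an assumed 3-fold higher control switching hazard, the ungated one-sided error is about 0.05 to 0.06 at PD 0.05 per month, 0.10 to 0.16 in the extreme case of no PD, and near nominal at PD 0.12 or with equal switching. The test and hazard ratio can be biased in either direction when switching differs by arm. The documents give neither switching nor PD rates.

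A reader might infer that the trial's error control is broken. The documents do not support that. OS is untouched, EFS is tested only after OS and the earlier-ranked endpoints, and with no effect on anything OS and EFS were both significant in at most 0.026 of simulated trials. The point should be fixed, but its reach is EFS and any subgroup endpoint that footnote b places below it.

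Treatment failure is also defined differently: Protocol 8.1.4.2 has "treatment failure defined as failure to achieve CR, CRi, PR, or MFLS" with no minimum number of cycles, while SAP 10.3.8 requires at least 6 cycles and does not list PR. This affects who counts as event-free and must be reconciled, but it is a separate point.

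**What to change.** Apply one rule to every event-free switcher, whatever happens later.

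1. **Primary, if PD and relapse are collected after new therapy:** count PD, confirmed relapse and death regardless of new therapy, keep survivors at risk through their own follow-up, and add an EFS exception to SAP 10.1. This matches the stated endpoint. The documents do not settle whether the data exist. Protocol 5.1.4 says patients are followed for PD and gives those stopping in CR, CRi, MLFS or PR two-monthly assessments, without saying that these continue after new therapy; for resistant disease it specifies survival calls. Appendix C marks disease assessment, but no bone marrow, at post-treatment follow-up.
2. **Sensitivity:** censor every event-free switcher at therapy start, including those who later die. State that this departs from death from any cause as an event and carries its own informative-censoring risk. It lost 9 to 30% of events in the runs (for example 161.6 to 143.7), with design-effect power 0.90 to 0.94 against 0.96 to 0.97 for rule 1.
3. **If PD after new therapy is not collected,** no rule is clearly best. Rule 1 applied without those data gave errors in favour of venetoclax from 0.001 to 0.110, and up to 0.228 against. Report at least rule 2 beside Table 4, and do not interpret the EFS medians and hazard ratio from Table 4 alone.

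If EFS has already been analysed, add these analyses as supplementary. Use the same structure in Table 5 (duration of CR + CRi, descriptive), which has the same split. The cost is wording in Tables 4 and 5, one exception in SAP 10.1 and modest reprogramming.
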